## f) Procedures Involved in the Human Research

All eligible participants will undergo study visits at screening, baseline (week 0), week 1, week 2, week 3, week 4, week 6, week 8, and week 12, (end of study).

Randomization will be conducted via a computer generated program and all study staff will be blinded unless un-blinding is required for safety reasons. Subjects will be randomized on a 1:1 ratio with stratification for concomitant antipsychotic status and depression at baseline (HRSD <8 vs  $\geq$  8). Study drug will be blinded and matched to placebo. Adapting from our previous work in BD and according to package labeling, the dosage titration schedule will be slow and flexible. Dosing will be initiated at 0.25 mg QHS on night one, followed by 0.25 mg BID day two onward, and increased every week to a target of 4.5 mg/day. As compared with our previous maximum 1.5 mg/day ([name] et al. 2012), we opted to allow up to 4.5 mg/day (the maximum approved dosage in Parkinson’s disease) to ensure adequate target engagement. We are familiar with this dose range, as 4.5 mg/day was allowed in our study in BD depression (Goldberg et al. 2004). Dosing will be flexible based on side effects; however, if 1.5 mg/day cannot be tolerated, the subject will be discontinued. Titration will occur up to week 6 and then efforts will be made to maintain the same dose until the completion of the trial (week 12).

Measures are described in detail below:

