**Primary hypothesis testing:** 100 participants will be randomized in a 1:1 allocation to treatment with pramipexole or placebo. The primary assessment of safety will be based on the incident of adverse event rates and standardized mood ratings at each visit. Differences in the incidence of individual adverse events will be compared between randomization arms using Poisson regression. Exact 95% confidence intervals (based on the Poisson distribution) for the risk ratios for individual adverse events for treatment with pramipexole versus placebo will be computed and may incorporate an estimated overdispersion parameter if observed variability exceeds that determined by the Poisson distribution. Performance on the IGT will also be used to track potential changes in impulse-control (baseline, weeks 6 and 12). We will test for correlations between IGT performance and mania symptoms at the times of testing (simultaneous measurements). Moreover, we will use IGT change scores as predictors in regression models to evaluate changes in mania ratings at concurrent time points as well as future time points. This will directly address the question of whether or not changes in IGT strategy serve as markers of current mania and/or impending affective destabilization.

The relative specificity of pramipexole in binding to D2/D3 receptors allows for a unique opportunity to enhance DA in neural networks associated with specific aspects of cognition as well a reward processing, which will be carefully assayed in this study so that exploratory analyses will be able to test questions related to the role for these receptors across several interacting domains in BD, at least at the level of behavior. Exploratory analyses will include specific domains and individual tasks which will be modeled to account for main effects and interactions (as described in primary analyses below).

The primary outcome for efficacy is change in cognition from baseline to week 6 (MCCB Composite). The null hypothesis is that there is no difference in this change between

|   |   |  |
|---|---|--|
|  | Protocol Title:                           | 1/2-Pramipexole in Bipolar Disorder: Targeting Cognition (PRAM-BD) |
|   | Principal Investigator Name/Contact Info: | [name]   |
|   | Primary Contact Name/Contact Info:        | [name]
[contact]                          |
|   | Date Revised:                             | March 23, 2016 – date of IRB approval May 6, 2017                  |

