**Sample size/Power:** A total of one hundred patients will be randomized 1:1 (50 from ISMMS, 50 from ZHH). The adequacy of this sample size is based on the ability to reject the null hypotheses of no difference between treatment groups with respect to the MCCB composite score with sufficient power (80%). Ideally, sample size would be determined to ensure adequate power to detect the minimal clinically important difference. No specific guidelines exist to establish such a threshold in this setting but cognitive change of at least a moderate effect would likely be necessary to allow for clinical meaningfulness. Our sample size provides approximately 80% power to detect a standardized difference (e.g., Cohen’s d) of approximately 0.55 with a two-tailed 0.05 level test. For the pre-specified subgroup analysis based on concomitant use at baseline, the detectable standardized difference is about 0.80.

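### Exact Poisson intervals for adverse-event risk ratios are too wide for common events if patients are counted; if occurrences are counted, the measure is a rate ratio and needs an exposure offset

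*Combined protocol and SAP*

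**What the plan says.** Section 5(h), Statistical Methods, under primary hypothesis testing, sets the safety analysis: "The primary assessment of safety will be based on the incident of adverse event rates and standardized mood ratings at each visit". The model is given next: "Differences in the incidence of individual adverse events will be compared between randomization arms using Poisson regression". The reported quantity is then described as "Exact 95% confidence intervals (based on the Poisson distribution) for the risk ratios for individual adverse events", and these intervals "may incorporate an estimated overdispersion parameter if observed variability exceeds that determined by the Poisson distribution".

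The same paragraph fixes the size: "100 participants will be randomized in a 1:1 allocation to treatment with pramipexole or placebo", so 50 per arm.

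The text does not say whether the analysis counts patients with at least one event or every occurrence. It speaks of rates in one sentence and of incidence and risk ratios in the next two. No offset, person-time or time at risk is named anywhere. Follow-up will vary: Section 5(f) states that "if 1.5 mg/day cannot be tolerated, the subject will be discontinued", and Section 5(j) also requires discontinuation when mood-scale thresholds are reached.

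**The concern.** A risk ratio compares proportions of patients affected. Each patient then contributes 0 or 1, with variance p(1−p). A Poisson model uses variance p, which is larger, and the gap grows with p. An interval built on it is therefore too wide for common events, and the dispersion clause cannot help because it acts only when variability is above Poisson.

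If occurrences are counted, the Poisson family is reasonable, but the measure is then a rate ratio and unequal time on study has to be allowed for.

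The pairing of methods is also loose. An exact Poisson interval has no free dispersion parameter, so adding an estimated one does not give a defined procedure.

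This comparison is part of the primary safety assessment. An interval that is too wide makes a real excess of a common side effect easier to read as no difference.

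**Working it through.** **Inputs.** 50 per arm and the 95% level come from Section 5(h). The documents give no adverse-event rates and no dropout by arm, so every event count and risk below is an assumption, shown over a range.

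**The plan's own figure.** The plan's power statements all concern efficacy, and none concerns adverse events. The main one is "approximately 80% power to detect a standardized difference (e.g., Cohen’s d) of approximately 0.55 with a two-tailed 0.05 level test". It reproduces: Φ(0.55 × √(50/2) − 1.96) = Φ(0.79) = 0.785. This confirms 50 per arm and has no other bearing on safety.

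**One worked case: 20 versus 10 patients, risk ratio 2.0.**

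- Exact Poisson: given 30 events in total, the pramipexole share π has Clopper–Pearson limits 0.4719 and 0.8271. With equal arms the ratio is π/(1−π), giving 0.4719/0.5281 = 0.89 and 0.8271/0.1729 = 4.78.
- Binomial (log-scale Wald): SE = √(1/20 − 1/50 + 1/10 − 1/50) = √0.11 = 0.332. Then exp(0.693 ± 1.96 × 0.332) = 1.04 to 3.83. The binomial score interval is 1.07 to 3.85.
- Poisson (log-scale Wald): SE = √(1/20 + 1/10) = √0.15 = 0.387, giving 0.94 to 4.27.

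On the log scale the planned interval is 1.29 times as wide as the binomial Wald interval. That factors as 0.387/0.332 = 1.17 from the Poisson assumption and about 1.10 from exactness. At equal risks in both arms the Poisson factor is 1/√(1−p): 1.05 at 10% and 1.41 at 50%.

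**Other counts out of 50 per arm.**

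| Patients | Exact Poisson | Binomial score | Fisher p |
|---|---|---|---|
| 10 vs 5 | 0.62–7.46 | 0.77–5.29 | 0.262 |
| 20 vs 10 | 0.89–4.78 | 1.07–3.85 | 0.049 |
| 24 vs 12 | 0.96–4.39 | 1.15–3.58 | 0.021 |
| 30 vs 18 | 0.90–3.17 | 1.10–2.61 | 0.027 |

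In the last three rows the planned interval includes 1 although Fisher's test, itself conservative, gives p below 0.05.

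**Separating the Poisson assumption from exactness.** All outcomes of two Binomial(50, p) arms were enumerated. Rejection by the Poisson test means that the planned interval excludes 1. Fisher's test is also exact, so the difference between the two isolates the Poisson assumption.

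| True risks | Exact Poisson | Fisher |
|---|---|---|
| 20% vs 5% | 0.48 | 0.51 |
| 30% vs 10% | 0.55 | 0.64 |
| 40% vs 20% | 0.35 | 0.52 |
| 50% vs 25% | 0.47 | 0.67 |

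The true two-sided type I error of the nominal 5% Poisson test is 1.6% at 10% risk, 1.5% at 20%, 1.0% at 30% and 0.3% at 50%.

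**Offset, if occurrences are counted.** The missing-data paragraph of Section 5(h) expects fewer than 10 patients to miss week 8. Take 9, all on pramipexole, with everyone else followed for 12 weeks and a constant event rate.

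- Leaving at week 2: mean exposure (41 × 12 + 9 × 2)/50 = 10.2 weeks and 10.2/12 = 0.85, so a true rate ratio of 2.0 appears as 1.70.
- Leaving at week 6: (41 × 12 + 9 × 6)/50 = 10.92 weeks and 10.92/12 = 0.91, so it appears as 1.82.
- Dropout balanced between arms: no attenuation.

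**The case against.** The best case for the plan is that it may mean to count occurrences. It speaks of rates, chooses Poisson regression and provides for overdispersion, and Section 5(f) has the side-effects checklist completed at every visit, so repeat events can be recorded. On that reading the Poisson interval is not inherently too wide and the dispersion clause is apt. This stands as a limit on the point, but it does not rescue the sentence: the measure would then be misnamed as a risk ratio, and exposure would need stating.

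Four stronger readings are tempting, and the documents do not support them.

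- *The overdispersion clause widens the interval further.* It applies only when variability exceeds Poisson. For 20/50 versus 10/50 the Pearson dispersion is (50 × 0.6 + 50 × 0.8)/98 = 0.71, so the clause would not be triggered. It fails to correct; it does not make matters worse.
- *All of the 29% extra width is due to the Poisson assumption.* About 17% is. The rest is the price of exactness, some of which an exact unconditional interval would also pay.
- *The missing offset hides substantial harm.* The text is silent on an offset and does not exclude one. At the expected attrition the effect is modest. Mood-related withdrawal applies to both arms, and an event that leads to withdrawal is still counted.
- *Harm will be missed because of this interval.* Safety also rests on mood ratings, suicidality ratings, vital signs, ECG, laboratory tests, review by the site investigators and DSMB review. No safety decision is tied to whether an interval excludes 1.

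**Conclusion.** The point holds in a limited form and should be corrected. If patients are counted, the stated interval method is wrong for the stated measure. The loss is material for common events: about 17 to 21 points of power against Fisher's test at control risks of 20% to 25% with a doubled risk on pramipexole. It is about 3 points at 20% versus 5%. These sizes rest on 50 per arm and assumed event risks.

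The offset issue is secondary and arises only if occurrences are counted. Attenuation is then 0% with balanced dropout, rising to about 15% if all 9 expected dropouts are on pramipexole and leave at week 2 or later.

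On either reading the sentence needs changing, because the unit is undefined and the exact interval with an estimated dispersion parameter is not a defined method.

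**What to change.** In Section 5(h), state the counting unit for individual adverse events and match the method to it.

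1. For patients with at least one event: report the risk ratio with a binomial score or exact unconditional 95% interval, or from Poisson regression with robust (sandwich) variance.
2. For occurrences, if these are analysed: call the measure a rate ratio, and use a Poisson or negative binomial model with log time on study as an offset.
3. Delete the combination of an exact interval with an estimated overdispersion parameter.

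The cost is SAP wording and minor analysis work in standard software. No new data are needed, since side effects are already recorded at every visit.

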### Clinical/Symptom Measures

- Structured Clinical Interview for the DSM-IV (SCID-IV) – (*screening*)
- Symptom rating scales: Young Mania Rating Scale (YMRS); Hamilton Rating Scale for Depression (HRSD); Brief Psychiatric Rating Scale (BPRS) – (*all visits*)
- Smoking questionnaire – (*screening, baseline, week 6, week 12*)

|   |   |  |
|---|---|--|
|  | Protocol Title:                           | 1/2-Pramipexole in Bipolar Disorder: Targeting Cognition (PRAM-BD) |
|   | Principal Investigator Name/Contact Info: | [name]   |
|   | Primary Contact Name/Contact Info:        | [name]
[contact]                          |
|   | Date Revised:                             | March 23, 2016 – date of IRB approval May 6, 2017                  |
|   | Study Number:                             | GCO 13-0237, HS 14-00328   |

Neurocognitive/Functional Measures

- Screening cognitive battery (see inclusion criteria 4.) – (*screening*)
- Cognitive assessment: MATRICS Consensus Cognitive Battery (MCCB- plus; see description below) – (*baseline, week 6, week 12*)
- The Probabilistic Stimulus Selection Task – (*baseline, week 6, week 12*)
- UCSD Performance Skills Assessment (UPSA) – (*baseline, week 12*)
- The World Health Organization Disability Assessment Schedule (WHODAS 2.0) – (*baseline, week 12*)

| The MATRICS Consensus Cognitive Battery | Domain               | Note/Description               |
|---|-----------------------------|---------------------------------------|
| Category Fluency                                      | Speed of Processing         | Total animals in 60 seconds           |
| BACS Symbol Coding                                    | Speed of Processing         | Matching numbers to symbols           |
| Trail Making Test Part A                              | Speed of Processing         | Dot-to-dot: Numbers only              |
| CPT-Identical Pairs                                   | Attention/Vigilance         | Computerized numeric stimuli          |
| Letter-Number Span                                    | Working Memory              | Recoding numbers and letters in order |
| WMS-III Spatial Span                                  | Working Memory              | Visual sequence forward and backward  |
| Hopkins Verbal Learning (HVLT)                        | Verbal Learning             | 12 word list x 3                      |

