## 6) Risks to Subjects

During the informed consent process, participants will be informed of the potential risks associated with the study. At each weekly visit the study physician will meet with participants and conduct a thorough review of symptoms including mood, and suicidal ideation. If there is an acute worsening of symptoms the study clinicians will review the case with the PI (or will make an emergency decision as needed) to ensure that the participant receives emergency care or hospitalization. Participation in the study will be discontinued in any case of clear symptom worsening. Between weekly visits, the participants will have emergency contact information.

Along with closely monitoring for symptom exacerbation, each visit with the study physician will entail a detailed side effect evaluation, which will include vital signs and a

|   |   |  |
|---|---|--|
|  | Protocol Title:                           | 1/2-Pramipexole in Bipolar Disorder: Targeting Cognition (PRAM-BD) |
|   | Principal Investigator Name/Contact Info: | [name]   |
|   | Primary Contact Name/Contact Info:        | [name]
[contact]                          |
|   | Date Revised:                             | March 23, 2016 – date of IRB approval May 6, 2017                  |
|   | Study Number:                             | GCO 13-0237, HS 14-00328   |

side effect checklist. The most common side effects of pramipexole are nausea, headache, dizziness, insomnia, constipation, muscle weakness, abnormal dreams, confusion, memory problems, urinary frequency. Participants will be educated about the potential for these side effects. Rare side effects have also been reported including sedating effects, impulse control symptoms (e.g. gambling), hallucinations, and orthostatic hypotension. The informed consent process will alert participants to these potential risks and close monitoring will ensure prompt response to any adverse effects with appropriate treatment and/or study discontinuation, as indicated.

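### The IGT regression for future mania cannot separate early warning from a concurrent association carried forward, because no adjustment for mania at the IGT visit and no reference visit are stated

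*Combined protocol and SAP*

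**What the plan says.** The analysis is described in section 5(h), under Statistical Methods, in the safety part of the paragraph on primary hypothesis testing. There are two steps. First, "We will test for correlations between IGT performance and mania symptoms at the times of testing (simultaneous measurements"). Second, "we will use IGT change scores as predictors in regression models to evaluate changes in mania ratings at concurrent time points as well as future" visits. The plan then states its inference: "This will directly address the question of whether or not changes in IGT strategy serve as markers of current mania and/or impending affective destabilization".

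The text gives a predictor (IGT change) and an outcome (change in mania rating). It does not say from which visit mania change is measured, and it lists no covariates.

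Three other places mention model terms, and none fills this gap:
- The preliminary-analysis paragraph of 5(h) allows covariates where needed, after comparing the groups on demographics, baseline symptoms and medication load.
- The concomitant-medication paragraph of 5(b) makes a medication load score a covariate.
- The MCCB efficacy model in 5(h) includes randomised group and the stratification indicators. That approach is extended to cognitive domains and reward-processing measures, not to a regression with mania as outcome.

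The IGT is given at baseline, week 6 and week 12. The Young Mania Rating Scale (YMRS) is scheduled at every visit.

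**The concern.** A claim of impending destabilization is useful only if IGT change says something about later mania that the mania rating on the same day does not. The matching null is no association between IGT change and later YMRS, given YMRS at the IGT visit. A regression on IGT change alone tests a different null: no association at all.

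Mania ratings persist from visit to visit. If IGT change merely mirrors mania at week 6, it will also correlate with later mania:
- With later change counted from baseline, that change contains the week 6 movement, so the slope is positive and reads as early warning.
- With later change counted from week 6, regression to the mean makes the slope negative and can hide real prediction.

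Arm is a second route. Section 6 lists impulse control symptoms among the rare side effects of the drug. If the drug moved both IGT and YMRS, patients pooled across arms would show an association even with none within arm.

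At stake is a safety statement: a false warning sign could be carried into later monitoring, or a true one missed.

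**Working it through.** **The plan's own figures.** None is given for this regression. The only power statement is for the MCCB comparison: 100 patients, d = 0.55, two-tailed 0.05. It reproduces: Φ(0.55 × √(50/2) − 1.96) = Φ(0.79) = 0.785, against a stated value of about 80%.

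**Inputs from the documents.** Total sample: "A total of one hundred patients will be randomized 1:1 (50 from ISMMS, 50 from ZHH"). The missing-data paragraph expects fewer than 10 patients lost to a visit, so I use N = 90. No level is stated for the IGT regressions; I borrow two-sided 0.05 from the MCCB test.

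**Assumptions, not in the documents.** Standardised YMRS at weeks 0, 6 and 12 (m0, m6, m12) is a first-order Markov series with visit-to-visit correlation φ of 0.5 or 0.7. Baseline-to-week-6 IGT change has correlation ρ of 0.3 or 0.5 with the part of m6 not explained by m0. IGT is scored so that a higher change goes with more mania. IGT adds nothing about m12 once m6 is known, so a test of added prediction should reject 5% of the time.

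**Implied correlation of IGT change with later mania change.**
- From baseline: Cov = φρ√(1−φ²) and Var(m12−m0) = 2(1−φ²), so r = ρφ/√2.
- From week 6: Cov = −(1−φ)ρ√(1−φ²) and Var(m12−m6) = 2(1−φ), so r = −ρ(1−φ)√((1+φ)/2).

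Rejection ≈ Φ(|z|−1.96) + Φ(−|z|−1.96), with z = atanh(r)√(N−3) and √87 = 9.327. For ρ = 0.3, φ = 0.5 from baseline: r = 0.15/1.414 = 0.106, z = 0.99, rejection = 0.167 + 0.002 = 16.8%.

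| ρ | φ | r, from baseline | rejects | r, from week 6 | rejects |
|---|---|---|---|---|---|
| 0.3 | 0.5 | 0.106 | 16.8% | −0.130 | 23.0% |
| 0.3 | 0.7 | 0.148 | 28.7% | −0.083 | 12.1% |
| 0.5 | 0.5 | 0.177 | 38.5% | −0.217 | 53.7% |
| 0.5 | 0.7 | 0.247 | 65.4% | −0.138 | 25.5% |

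Simulated regressions agree: 17% to 67% from baseline, nearly all positive, and 12% to 55% from week 6, nearly all negative. With m6, m0 and arm in the model, simulated rejection is about 5%.

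**A different coding of the concurrent link.** Let IGT change correlate ρ with the raw change m6−m0. Then r = ρ√(1+φ)/2 from baseline and −ρ(1−φ)/2 from week 6. With N = 100 and φ = 0.5, ρ = 0.3 gives r = 0.184 and −0.075, with simulated rejection 45.2% and 11.7%. ρ = 0.5 gives r = 0.306 and −0.125, with 88.4% and 23.1%. The sizes move but the signs do not. Under this coding, adding m6 alone to the change-from-baseline model still leaves 45.8% (ρ = 0.3), so baseline YMRS is needed too.

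**When prediction is real.** Suppose later YMRS rises 0.3 SD per SD of IGT change, with ρ = 0.3. Simulated power for change from week 6 is 36% unadjusted and 85% adjusted at φ = 0.5. At φ = 0.7 it is 81% and 95%.

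**Arm alone.** Take ρ = 0, φ = 0.5, N = 100 and a drug shift of d SD on both measures. For change from baseline, r = (d²/4)/√((1+d²/4)(2(1−φ²)+d²/4)). At d = 0.5 this is 0.0625/√(1.0625 × 1.5625) = 0.048, and rejection is 7.7%. Simulation gives 5.5%, 7.7% and 21.2% for d = 0.3, 0.5 and 0.8. For change from week 6 with a constant drug effect it stays at about 5%.

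**Measurement error.** If YMRS has reliability 0.7 to 0.8 (assumed), adjusting for the observed m6 does not fully hold true mania fixed. The adjusted model then rejects about 6% to 16% of the time under the same null (N = 90).

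**The case against.** Several objections have force.

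- **The plan is silent; it does not declare an unadjusted, pooled model.** A reader might infer that it commits to one. It does not: it speaks of regression models in the plural and allows covariates elsewhere. This stands. But the covariate clauses concern baseline features and medication load, and do not reach week 6 mania or arm. The reference visit is undefined under any reading.
- **The wording does not demand added value over current mania.** The plan asks "whether or not changes in IGT strategy serve as markers of current mania and/or impending affective destabilization". A measure that tracks persistent mania does predict later mania in the plain sense. So the stronger claim, that the test rejects for a concurrent association instead of for prediction, is not supported: it also rejects for true prediction. What remains is that the explanations cannot be told apart, while the plan says the question is answered directly.
- **The sizes rest on assumed correlations.** They do, and they shift with how the concurrent link is coded. The sign reversal does not depend on that choice.
- **Confounding by arm is minor.** Agreed. It is small at 0.5 SD on both measures and absent in one version of the outcome. It should not be read as an equal fault.
- **Adjustment is not a complete cure.** Also agreed: a return to exactly 5% requires error-free YMRS.

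**Conclusion.** The concern holds as a gap in specification. Without mania at the IGT visit in the model and without a defined reference visit, the future-time-point regression cannot support the statement about impending destabilization. With no added prediction it rejects about 17% to 67% of the time with a positive slope (change from baseline) or about 12% to 55% with a negative slope (change from week 6). The answer can therefore change sign with a choice left open. A drug effect on both measures is a secondary and smaller source.

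The figures assume concurrent correlation 0.3 to 0.5, YMRS correlation 0.5 to 0.7 and N = 90. They ignore the floor and skew of YMRS in patients who enter below 8, and discontinuation at YMRS 15 or above.

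A reader might infer that the trial's main conclusions are at risk. They are not: this analysis supports the safety assessment, which rests primarily on adverse events and mood ratings. No withdrawal criterion uses the IGT, and the primary MCCB test is untouched. Severity is low to moderate.

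**What to change.** In section 5(h), replace the sentence on IGT change scores with two stated models:

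1. **Concurrent:** YMRS at the IGT visit on IGT change from baseline, with baseline YMRS, randomised group and the two stratification factors (antipsychotic use, baseline depression status).
2. **Future:** YMRS at week 12, with week 8 as supportive, on baseline-to-week-6 IGT change, with week 6 YMRS, baseline YMRS, randomised group and the stratification factors. Only this IGT change score has later mania ratings to predict.

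Using the later YMRS value as outcome, with both earlier values as covariates, removes the reference-visit ambiguity. Rest any statement about impending destabilization on the IGT coefficient in model 2 alone. Report it as exploratory, noting that measurement error in YMRS leaves some residual confounding.

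The cost is wording only, since every term is already collected. The price is a few degrees of freedom and a smaller apparent association if IGT change only mirrors current mania.
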